3.2 Analysis Populations

3.2.1 *Intent-to-Treat (ITT) Population*

The ITT Population is defined as all patients who were randomized, regardless of whether they received any study drug.

3.2.2 *Safety Population*

The Safety Population is defined as all randomized patients who receive any amount of study drug. All safety data will be analyzed using the Safety Population. In the event that a patient is administered incorrect study drug (e.g., not administered the study drug assigned at randomization), the actual treatment received will be used for safety analyses. For patients who intermittently receive incorrect study drug, they will be included in the eptetaborole group if they receive any eptetaborole.

3.2.3 *Micro-ITT Population*

The Micro-ITT Population is defined as all patients who meet the definition for the ITT Population and have MAC culture-positive Pre-Study and Screening respiratory specimens (per Inclusion Criterion 3a). Primary endpoint analyses in both Phase 2 and Phase 3 parts of the study will be performed in this patient population. A Sponsor internal Data Review Committee (DRC) will review deviations of this inclusion criterion to make a final determination of the Micro-ITT Population according to details outlined in a separate Evaluability Review Plan.

3.2.4 *Per-Protocol (PP) Population*

The PP Population is defined as all patients in the ITT Population who completed the study with no important protocol deviations that may impact the primary efficacy assessment. Separate protocol deviation reviews will assess each deviation as important or non-important and, if important, whether they impact the primary efficacy endpoint, prior to each formal database lock and analysis. The PP Population will be a secondary population for analysis of the primary efficacy endpoint and key secondary endpoints.

The Sponsor DRC will review study data and important protocol deviations for determination of patient inclusion in the PP Population according to criteria outlined in a separate Evaluability Review Plan. Formal DRC data reviews will occur on a regular basis throughout the study. DRC members and decisions taken during the meetings will be documented in minutes and/or as comments in a PP review spreadsheet. The DRC members will be blinded to treatment assignment for all data reviews. Immediately prior to database lock and unblinding of each formal analysis as described in Section 2.2.6 ([Analysis Timing](#)), the final approved spreadsheet and SAS dataset are created using treatment-specific variables. Inclusion in the PP Population will be considered locked at database unblinding and may only be changed programmatically. Any instances of receipt of incorrect study drug will be determined programmatically after database lock and unblinding.

3.2.5 *Pharmacokinetics (PK) Population*

The PK Population is defined as all patients treated with at least 1 dose of eptraborole and at least 1 analyzable PK sample.

3.2.6 *Full Analysis Set-PRO (FAS-PRO) (applicable to Phase 2 part only)*

The psychometric analyses will be conducted using blinded data from the FAS-PRO, and all available data will be included. The Full Analysis Set is identical to the ITT Population. The FAS-PRO will include all randomized patients who have MACrO₂ PRO data at Screening and Day 1 (for test-retest reliability assessment), and at Day 1 and at least Month 3 and/or Month 6 (for all other calculations).

3.2.7 *Embedded Interview Population (applicable to Phase 2 Part only)*

Up to 40 Phase 2 patients who meet Micro-ITT Population and interview eligibility criteria (see protocol Section 7.5.6).

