3.1.1. Duration of Study Drug Administration and Study Participation

For the Phase 2 and Phase 3 parts of the study, the duration of study participation for each patient, not including Screening, will be up to approximately 19 months as described in [Section 3.1](#).

Each patient's duration of study participation will vary depending on the timing of microbiological sputum MAC culture conversion. To receive study drug beyond Month 6, a patient must have achieved a microbiological sputum MAC culture conversion.

All patients will receive a minimum of 6 months of blinded study drug treatment. At the Month 6 Visit, all available sputum culture results will be assessed by the Investigator to determine whether a patient is a converter or non-converter. A converter is defined as a patient who has 3 consecutive monthly MAC-negative sputum cultures at any time within the first 6 months of the study. A non-converter is a patient who does not have 3 consecutive monthly MAC-negative sputum cultures at any time within the first 6 months of the study.

Patients who are assessed as converters will continue taking blinded study drug for 12 months after the first month that defines sputum culture conversion, up to a maximum of 16 months. Patients who are assessed as non-converters will discontinue study drug at the Month 6 Visit. Patients who are discontinued from study drug at the Month 6 Visit will complete the EOT Visit at this time point, as well as the MACrO₂ and PGIS 1 week (+1 day) after their EOT Visit, and an LFU Visit 3 months (84 days \pm 14 days) after the last dose of study drug.

Because reporting of final respiratory culture and identification results may occur up to 8 weeks after specimen receipt at the regional or central microbiological laboratory, it is unlikely that the Month 5 culture results will be available at the Month 6 Visit. Patients who have negative culture results from Month 4 and no culture data available from Month 5 will be presumed to be converters and will continue blinded study drug at the Month 6 Visit. Such patients subsequently found to have positive cultures from the Month 5 and/or Month 6 visit must be discussed with the Medical Monitor for determination of continued study drug therapy beyond Month 6. Patients with *missing* sputum cultures from any visit prior to Month 6 should not be prematurely

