4.3. Withdrawal from Study

Participation of a patient in this clinical study may be discontinued for any of the following reasons, including, but not limited to:

- The patient withdraws consent or requests discontinuation from the study for any reason
- The patient is lost to follow-up (see [Section 4.5](#))
- The patient fails to comply with Protocol requirements or study-related procedures
- The Investigator determines that it is in the best interest of the patient to withdraw from the study Protocol, for reasons other than an AE (eg, an occurrence of any medical condition or circumstance that exposes the patient to substantial risk and/or does not allow the patient to adhere to the requirements of the Protocol)

- The study is terminated or temporarily suspended by the Sponsor or a regulatory authority (see [Section 8.4](#))

Patients who wish to withdraw completely from this study during the Treatment Period should be encouraged to undergo the EOT Visit safety and efficacy assessments at the time of withdrawal at an ET Visit.

Patients who withdraw from the study should be assessed as indeterminate at the most appropriate visit(s) at the time of withdrawal.

Patients who are withdrawn from the study will not be replaced.

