8. STATISTICS

8.1. Analysis Populations

The following analysis populations will be defined in this study:

- Intent-to-Treat (ITT) Population: All patients who were randomized, regardless of whether they received any study drug
- Safety Population: Randomized patients who received any amount of study drug
- Micro-ITT Population: Patients who meet the definition for the ITT Population and have MAC culture-positive *Pre-Study* and *Screening* respiratory specimens (per Inclusion Criterion 3.a). Primary efficacy endpoint analyses in both Phase 2 and Phase 3 parts of the study will be performed in this patient population.
- Per-Protocol Population: Patients who meet the definition for the ITT Population and have no important protocol deviations that would affect the assessment of the primary efficacy outcome
- PK Population: All patients treated with at least 1 dose of epetraborole and who have at least 1 analyzable PK sample
- Full Analysis Set-PRO (FAS-PRO) (applicable to Phase 2 part only): The psychometric analyses will be conducted using blinded data from the FAS-PRO, and all available data will be included. The Full Analysis Set is identical to the ITT Population. The FAS-PRO will include all randomized patients who have MACrO₂ PRO data at Screening and Day 1 (for test-retest reliability assessment), Day 1, and at least Month 3 and/or Month 6 (for all other calculations).
- Embedded Interview Population (applicable to Phase 2 part only): Up to 40 Phase 2 patients who meet Micro-ITT Population and interview eligibility (per [Section 7.5.6](#))

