1 INTRODUCTION

This Statistical Analysis Plan (SAP) provides a description of the statistical methods to be implemented for the analysis of data from Study EBO-301 (Protocol Version 5.0, dated 07 June 2023), entitled “A Phase 2/3, Randomized, Double-Blind, Placebo-controlled, Multicenter, Prospective Study to Assess the Efficacy, Safety, and Pharmacokinetics of Orally Administered Epetraborole in Patients with Treatment-refractory *Mycobacterium avium* Complex Lung Disease (MACrO₂),” which was intended as a single study to support registration. EBO-301 was designed as a seamless trial randomizing patients to either treatment with epetraborole plus an optimized background regimen (OBR) or placebo plus an OBR, with no pause between Phase 2 and Phase 3 enrollment. Phase 2 enrollment was completed in September 2023 (n=80), at which time enrollment in the Phase 3 part of the trial started immediately.

On 08 August 2024, the Sponsor terminated the trial based on topline, unblinded results from the Phase 2 part of the study and notified the Agency accordingly. The Phase 2 study met its primary objective of demonstrating the ability to validate the MACrO₂ PRO and showed a preliminary efficacy signal favoring epetraborole based on a responder analysis (39.5% [15/38] epetraborole vs 25% [10/40] placebo, p=0.19). However, the epetraborole plus OBR arm was not superior to the placebo plus OBR arm in sputum culture conversion rate. Nonetheless, the Sponsor is continuing with an analysis of the Phase 3 study data because of the positive Phase 2 clinical efficacy data noted.

This SAP supports the planned analyses of the primary, secondary, and exploratory efficacy and safety endpoints identified for evaluation both in the United States (US) by the Food and Drug Administration (FDA) as well as for other regulatory agencies outside the US. In accordance with the above protocol, any primary or secondary objectives or endpoints and hierarchical testing procedures that differ between regions will be specifically designated by “in the US” for FDA regulatory interpretation or “outside the US” for other regulatory agency interpretation in this document.

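### SAP 3.2.4 adds an undefined study-completion condition to the Per-Protocol population, so membership can turn on follow-up after Month 6 that is planned to be longer for converters

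*SAP*

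**What the plan says.** **Two definitions.** Protocol 8.1 defines the Per-Protocol (PP) population as: "Patients who meet the definition for the ITT Population and have no important protocol deviations that would affect the assessment of the primary efficacy outcome". SAP 3.2.4 says: "The PP Population is defined as all patients in the ITT Population who completed the study with no important protocol deviations", the deviations being those that may affect the primary efficacy assessment. It makes PP a secondary population for the primary and key secondary endpoints. It leaves the inclusion criteria to a separate Evaluability Review Plan, applied by a blinded committee, and fixes membership at unblinding. SAP Section 5, which lists departures from the protocol's analyses, does not mention the added condition.

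**Completion.** Protocol 9.3 defines completion only for the study as a whole, by the last patient's LFU. SAP 3.3.1 tabulates completing study drug separately from completing the study, and the latter only at the end-of-study analysis.

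**Follow-up.** Protocol 3.1.1: "Patients who are assessed as converters will continue taking blinded study drug for 12 months", counted from the first month of the converting run and capped at 16 months in total. Non-converters stop at Month 6. LFU is 84 ± 14 days after the last dose in both cases.

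**Dates.** SAP Section 1: "Phase 2 enrollment was completed in September 2023 (n=80), at which time enrollment in the Phase 3 part of the trial started immediately". And: "On 08 August 2024, the Sponsor terminated the trial based on topline, unblinded results". Protocol 4.3 includes among the reasons a patient's participation may end: "The study is terminated or temporarily suspended by the Sponsor or a regulatory authority".

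**Use of PP in Phase 3.** It is the sensitivity population for the QOL-B respiratory domain analysis (SAP 3.4.3.1). It is also used for the other continuous PROs and the PRO responder analyses (3.4.3.3) and for the repeated-measures models (3.4.3.4).

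**The concern.** A per-protocol set is meant to show whether the result holds among patients treated and assessed as planned up to the endpoint. All three endpoints in the Phase 3 testing order (SAP 3.4) are settled by Month 6. Whether a patient later attends LFU cannot change the Month 6 score, so a completion condition removes evaluable patients for reasons unrelated to the endpoint.

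The condition is also not neutral. How long a patient must stay in order to complete depends on culture conversion, which is a post-randomization outcome and itself one of the tested endpoints. When a trial is stopped at a fixed calendar date, a longer required follow-up means a lower chance of completing. Depending on how completion is read, PP membership could therefore depend on conversion and on enrolment date. The sample-size rationale in Protocol 8.2.4.2 assumes that conversion and symptom improvement are correlated, so selecting on conversion could carry into the QOL-B and other PRO comparisons. Blinded committee review would not remove this, because the selection acts through the outcome and not through knowledge of treatment.

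**Working it through.** **1. Reproduce the plan's own duration.** The latest first-negative month that still allows three consecutive monthly negatives by Month 6 is Month 4. Treatment is 4 + 12 = 16 months, and LFU adds 3, giving 19 months. This matches the stated maximum of 16 months on drug and about 19 months in the study.

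**2. Study day of planned LFU** (28-day months, as in the schedule of assessments).
- Non-converter: last dose Day 169; LFU 169 + 84 = Day 253. With windows, 162 + 70 = Day 232 to 176 + 98 = Day 274.
- Earliest converter (first negative at Month 1, Day 29): last dose 29 + 12 × 28 = Day 365; LFU 365 + 84 = Day 449. With every window at its shortest, 22 + 336 = Day 358 and 358 + 70 = Day 428.
- Latest converter (first negative at Month 4, Day 113): last dose 113 + 336 = Day 449; LFU Day 533.

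**3. Place these on the calendar.** The SAP gives the Phase 3 start only as September 2023. Assume Day 1 on 1 September 2023, the date most favourable to completion.
- 8 August 2024 is 342 days later, Study Day 343. With Day 1 on 30 September it would be Day 314.
- Earliest converter: last dose 30 August 2024, LFU 22 November 2024. Shortest windows: 23 August and 1 November 2024. All fall after termination.
- Non-converter: LFU by 8 August 2024 needs Day 1 on or before 8 August 2024 − 252 days = 30 November 2023 (9 November to 21 December 2023 across the windows).
- Nominal Month 6 by 8 August 2024 needs Day 1 on or before 8 August 2024 − 168 days = 22 February 2024. Patients who started between about 30 November 2023 and 22 February 2024 could have Month 6 data without having reached LFU, even as non-converters.

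**4. Apply the two possible readings of completion.**
- *Reading A: patients still in the study at termination are non-completers.* No converter on the planned course enters PP. Non-converters enter only if they started by about 30 November 2023.
- *Reading B: drug stopped at termination and LFU done afterwards counts as completing.* Stopping on 8 August 2024 puts LFU at 8 August + 70 to + 98 days, that is 17 October to 14 November 2024. This is before SAP Version 3.0 (15 April 2025), and converters can enter PP.

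**5. How far the readings differ at planning rates (illustration only).** With 124 and 62 Micro-ITT patients and conversion of 30% and 10%, Reading A would remove 0.30 × 124 = 37.2 epetraborole and 0.10 × 62 = 6.2 placebo patients as converters. That leaves at most 186 − 43.4 = 142.6, before any loss of later-enrolled non-converters. The documents do not give the number enrolled in Phase 3 at termination, so this is not a forecast. SAP Section 1 also reports that epetraborole was not superior on conversion in Phase 2, so the imbalance between arms could be much smaller. No effect on the QOL-B estimate can be calculated from the documents.

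**The case against.** The strongest reply is that nothing shows converters were excluded. Protocol 3.1, 3.1.1 and 4.4 keep patients who stop drug early in the study for End of Therapy and LFU. SAP 3.3.1 separates drug completion from study completion. SAP 3.4, revised after termination, still plans a single Phase 3 analysis through LFU. Protocol 4.3 says participation may be discontinued for the listed reasons, not that everyone was withdrawn on 8 August 2024. The Evaluability Review Plan, which holds the working criteria, is not among the documents. The SAP's own use also suggests that completion was not meant literally: PP analyses were planned at the Phase 2 Month 6 analysis (3.4.1.1, 3.4.1.3), before study completion could be known for everyone.

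This stands. A reader might infer that the definition excludes converters as a matter of fact, and the documents do not support that. A reader might also infer that conversion in PP would be near 0% in both arms. That needs Reading A and also a PP analysis of conversion, and SAP 3.4.3.2 specifies Micro-ITT only for that endpoint; only the general sentence in 3.2.4 points the other way.

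A further tempting step is to require that PP be drawn from Micro-ITT. The ITT base is the protocol's own definition, and deviations from Inclusion Criterion 3a already go to the committee, so this is not a SAP departure.

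The reply does not answer the remaining points. The added condition is absent from the protocol, is not listed as a change, is undefined for a patient in a terminated trial, and reaches past the endpoint. The Phase 2 inconsistency is itself a sign that the text needs correcting.

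**Conclusion.** The point holds in limited form. SAP 3.2.4 narrows the protocol's PP definition with a condition that is undefined, is not recorded in Section 5, and depends on events after Month 6. Under one available reading it selects on conversion and enrolment date; under the other it need not. Version 3.0 was issued after termination and does not choose between them.

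The date arithmetic rests on a Phase 3 start no earlier than 1 September 2023, 28-day months and the planned treatment course. Reading A further assumes that termination on 8 August 2024 ended follow-up, which the documents do not state.

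The reach is the PP sensitivity analysis of the US primary QOL-B endpoint and the other PP PRO analyses. A reader might take this as undermining the primary result. It does not: the primary analyses use Micro-ITT, PP has no place in the hierarchical testing, and no alpha or decision rule changes. Severity is minor to moderate.

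**What to change.** In SAP 3.2.4, delete the words *completed the study* and restore the protocol condition, that patients "have no important protocol deviations that would affect the assessment of the primary efficacy outcome", with deviations judged on data through Month 6. Keep the ITT base as in the protocol. Add one sentence stating that sponsor termination after Month 6 is not a reason for exclusion from PP. Align the Evaluability Review Plan with this wording.

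If the sponsor prefers to keep a completion condition, define it at patient level for Phase 3 as completion through Month 6 and list it in Section 5 as a change from the protocol.

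The cost is one or two sentences in the SAP and a matching edit to the review plan. No new data or analyses are needed. It should be done before PP membership is locked, since 3.2.4 fixes membership at unblinding.

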7.5.3.2. Collection and Testing During Screening

Two to 3 expectorated or induced *Screening* sputum samples should be collected within the 8 week Screening Period (after the ICF is signed). If a patient is unable to produce sputum spontaneously, 1 induced sputum specimen at the site will be acceptable. Sputum samples may be collected on the same day or within a 5-day window beginning with collection of the first sample. The *Screening* sputum samples will be sent to the regional or central microbiological laboratory for mycobacterial culture, identification, and quantification. Susceptibility testing and molecular testing (if applicable) of isolates will be performed at the central microbiology laboratory. The 8-week Screening Period allows for culture and identification of MAC isolates. Only identification to MAC level is required for randomization. Antimycobacterial susceptibility and molecular testing results (if applicable) are not required prior to randomization. See the Laboratory Manual and testing details in [Section 7.5.3.4](#).

If the *Pre-Study* MAC-positive respiratory specimen was collected >8 weeks to 6 months prior to signing the ICF, the patient may be enrolled only after at least 1 of the *Screening* sputum samples is reported as MAC-positive by the regional or central microbiological laboratory.

If the *Pre-Study* MAC-positive respiratory specimen was collected within 8 weeks prior to signing the ICF and the patient was taking OBR at the time the specimen was collected, the patient may be enrolled in the study (at the Investigator's discretion) after collection of the *Screening* sputum sample(s) and a pending *Screening* culture result. If the *Screening* sputum sample culture(s) is finalized as MAC-negative *after* randomization, the patient will be

prematurely discontinued from study drug at the time that the final *Screening* sputum culture is reported as negative, and their OBR will be continued at the Investigator's discretion; however, they will remain in the study (ie, they will not be withdrawn from the study) to undergo all scheduled EOT and LFU assessments, including safety assessments.

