3.4.3 Phase 3 Efficacy Endpoints

3.4.3.1 Phase 3 Primary Efficacy Endpoint in the US (Key Secondary Endpoint Outside the US)

The primary efficacy endpoint in the US (key secondary outside the US) is change from baseline to Month 6 in QOL-B respiratory domain score. The Estimand corresponding to the primary endpoint is defined with the following five attributes:

1. Population: Patients with MAC culture-positive Pre-Study and Screening respiratory specimens
2. Treatment: Epetraborole oral tablets 500 mg (two 250 mg oral tablets) QD + OBR or placebo oral tablets QD matched to epetraborole dosage + OBR
3. Variable: Change from baseline to Month 6 in QOL-B respiratory domain score. QOL-B respiratory domain score is measured on a scale from 0 to 100 (with higher scores indicating better health-related quality of life). The baseline QOL-B respiratory domain score assessment is defined as the last entry recorded or updated by the patient on or prior to the first dose of study drug + 1 day (ePRO-specified close of window to further entry to patients).
4. Intercurrent events:
 - a. New, additional non-study-specific, antimycobacterial therapy that is potentially effective against MAC for reasons other than clinical failure of study drug: data collected after such therapy will be set to the last available score from a visit prior to the start of therapy (composite strategy)
 - b. Surgery for MAC lung disease for reasons other than clinical failure of study drug: data collected after such surgery will not be used and results will be set to the last available score from a visit prior to surgery (composite strategy)
 - c. Permitted medications/interventions or prohibited medications/interventions other than those described in bullets a and b: QOL-B respiratory domain data collected after permitted or other prohibited medications/interventions administration will be used as recorded (treatment policy strategy)
 - d. Inadequate compliance: patient data will be used as recorded (treatment policy strategy)

5. Population-level summary: Difference between epetraborole + OBR and placebo + OBR in least squares mean change from baseline to Month 6 in QOL-B respiratory domain score.

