QOL-B respiratory domain scores are measured on a scale from 0 to 100 (with higher scores indicating better health-related quality of life). QOL-B respiratory domain scores will be summarized by visit in the Micro-ITT Population. Descriptive statistics of both the reported QOL-B respiratory domain scores and change from baseline will be reported by visit (monthly through Month 6). Change from baseline to Month 6 in QOL-B respiratory domain score will be analyzed using an analysis of covariance (ANCOVA) model, including baseline score, treatment and either including (primary analysis) or excluding (sensitivity analysis 1) stratification factors of baseline ALIS use and the presence or absence of any fibrocavitary disease as covariates. Least squares means, 95% confidence intervals, and p-values of the treatment comparison will be presented for both the Micro-ITT (primary) and PP (sensitivity) populations.

Patients who fail to provide a complete QOL-B respiratory domain score at both baseline and Month 6 will be excluded from the analysis and considered unbiased under the missing at random (MAR) assumption, with the exception of patients experiencing intercurrent events, which will be accounted for following the imputation rules above. However, in an additional pair of sensitivity analyses, the primary efficacy analysis will be repeated as described above, but applying a treatment policy strategy in which results for patients with new, additional non-study-specific, antimycobacterial therapy that is potentially effective against MAC, or surgery for MAC lung disease, for reasons other than clinical failure of study drug, will be used as recorded. These models will be run using the ANCOVA model as described above, including baseline score, treatment and either including (sensitivity analysis 2) or excluding (sensitivity analysis 3) stratification factors of baseline ALIS use and the presence or absence of any fibrocavitary disease as covariates.

3.4.3.2 Phase 3 Primary Efficacy Endpoint Outside the US (Key Secondary Endpoint in the US)

The primary efficacy outside the US (secondary in the US) is by-patient sputum culture conversion monthly through Month 6. The Estimand corresponding to the primary endpoint is defined with the following five attributes:

1. Population: Patients with MAC culture-positive Pre-Study and Screening respiratory specimens

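### The Per-Protocol set is built from ITT rather than Micro-ITT, so no written rule removes patients whose pending Screening culture proves MAC-negative (minor)

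*SAP*

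**What the plan says.** **Per-Protocol set.** SAP 3.2.4: "The PP Population is defined as all patients in the ITT Population who completed the study with no important protocol deviations", limited to deviations that bear on the primary efficacy assessment. Protocol 8.1 uses the same starting set without the completion condition: "Per-Protocol Population: Patients who meet the definition for the ITT Population and have no important protocol deviations", again limited to those affecting the primary outcome.

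**Target population.** Both Phase 3 estimands in SAP 3.4.3 give the same first attribute: "Population: Patients with MAC culture-positive Pre-Study and Screening respiratory specimens". Those patients form the Micro-ITT Population of SAP 3.2.3.

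**Pending-culture route.** Inclusion Criterion 3.a refers to Protocol 7.5.3.2 for enrolment on a pending Screening culture. There, a patient whose positive Pre-Study specimen was collected within 8 weeks before consent and who "was taking OBR at the time the specimen was collected, the patient may be enrolled in the study" at the Investigator's discretion. If the Screening culture is finalised as negative after randomisation, the patient is "prematurely discontinued from study drug at the time that the final" Screening result is reported. However, "they will remain in the study (ie, they will not be withdrawn from the study) to undergo all scheduled EOT and LFU assessments".

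**Use of the PP set in Phase 3.** For the US primary endpoint, the ANCOVA results "will be presented for both the Micro-ITT (primary) and PP (sensitivity) populations". SAP 3.4.3.3 also runs the PRO responder comparisons in PP, and SAP 3.4.3.4 runs the exploratory MMRM there. SAP 3.4.3.2 describes culture conversion only in Micro-ITT.

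**The concern.** A per-protocol analysis is normally read as the primary population restricted to patients who adhered to the plan. Here PP is not nested in the primary population. A patient who came in through a permitted route, stopped drug because the protocol required it, and attended EOT and LFU meets every PP condition written in the SAP. That patient is outside the estimand population and had study drug withdrawn by design.

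If such patients are included, a difference between PP and Micro-ITT results reflects a change of population as well as adherence. In the responder comparisons they would tend to be scored as non-responders in both arms, which narrows the difference. In the MMRM they add early visits from people whom the estimand excludes.

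**Working it through.** **1. Can such a patient meet the written PP conditions?**
- Randomised: yes, so in ITT.
- Completed the study: possible. Protocol 7.5.3.2 keeps the patient through LFU, and SAP 3.3.1 counts study completion separately from study drug completion.
- No important deviation: not settled by the text. The route is permitted, but SAP 3.2.3 speaks of deviations from this criterion, reviewed by the data review committee to settle Micro-ITT membership.
- Express exclusion: none found. Protocol 5.8.3 does exclude recipients of prohibited therapy from PP, with no matching line for a negative Screening culture. The Embedded Interview Population is nested in Micro-ITT; PP is not.

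**2. Which PP analyses would they reach?** Inputs: final culture up to 8 weeks after receipt (Protocol 4.4); LFU 84 ± 14 days after last dose; Month 6 at Day 169 ± 7.
- A sample received about Day 1 is final by about Day 57 (1 + 56).
- LFU: 57 + 84 = Day 141, range 127 to 155.
- Month 6 window: Day 162 to 176.

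LFU therefore comes before Month 6, and an earlier result moves it earlier still. The Month 6 ANCOVA drops patients without a Month 6 score (SAP 3.4.3.1), so most of these patients leave it. In the responder comparisons, SAP 3.1.4 counts missing Month 3 or Month 6 QOL-B, NTM and SGRQ-C scores as non-response. The MMRM retains patients with missing visits, so their early visits count.

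**3. The plan's own figures.** Protocol 8.2.4.2 assumes 30% versus 10%, two-sided alpha 0.05, and 124 versus 62 patients, with about 90% power.
- Normal approximation: 0.897.
- Exact enumeration of the unstratified Miettinen-Nurminen test: 0.907. The stated power is reproduced.
- Inflation for 20% exclusion: 186 / 0.80 = 232.5, so 233, or 234 at 2:1. Reproduced.

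**4. Dilution of a PP responder difference.** Let f be the share of the PP set outside Micro-ITT, all counted as failures. The rates become 30%(1 − f) and 10%(1 − f), so the difference is 20(1 − f) points. It is the same for any response rate common to both arms.

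| Case | f | Epetraborole | Placebo | Difference | Loss |
|---|---|---|---|---|---|
| None enter | 0 | 30.0% | 10.0% | 20.0 | 0 |
| Phase 2 shortfall, (80 − 78)/80 | 2.5% | 29.25% | 9.75% | 19.5 | 0.5 |
| All planned exclusions, (234 − 186)/234 = 48/234 | 20.5% | 23.8% | 7.9% | 15.9 | 4.1 |

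The 78 is 38 + 40, the responder denominators in SAP Section 1.

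**5. After nesting PP in Micro-ITT.** The planned maximum of the PP set falls from 234 to 186, and patients outside the estimand population fall from at most 48 to 0. No primary sample size, power or alpha figure changes.

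**The case against.** The strongest reply is that a gatekeeper exists. SAP 3.2.4 gives PP membership to a blinded Sponsor data review committee under an Evaluability Review Plan, and SAP 3.3.2 refers deviation categories to a separate Protocol Deviation Plan. Neither is supplied. Criterion 3.a still asks for a positive Screening sample; the pending route lets enrolment precede the result but does not say that a negative result meets the criterion. The committee may well exclude these patients. This stands: entry is possible, not established. It does not remove the point, because an intended exclusion belongs in the population definition.

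The analyses that remain exposed carry little weight. The MMRM is exploratory, and the responder comparisons lie outside the three-endpoint hierarchy. This also stands.

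The dilution figures are soft. The 30% and 10% rates were set for a responder endpoint that is no longer the US primary. The documents do not say how many Phase 3 patients were randomised before termination, so 234 is only the plan. The failure rule in PP is also unclear: SAP 3.1.4 names no population for QOL-B, NTM and SGRQ-C, limits the MACrO₂ symptom rule to Micro-ITT, and SAP 3.4.3.3 ties failure to the Micro-ITT analysis.

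A reader might infer that the PP sensitivity analysis of the US primary endpoint is compromised, or that any PP versus Micro-ITT contrast becomes uninterpretable. The documents support neither. The timing removes most of these patients from the Month 6 ANCOVA, and SAP 3.3.1 requires a listing of each patient's inclusion in or exclusion from Micro-ITT and PP, with reasons, so they can be identified. Nor is attenuation shown for the MMRM, where these patients would contribute mainly early visits, largely recorded on drug.

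**Conclusion.** The point holds as a defect in a secondary population definition, and it is minor. In both documents PP starts from ITT, and no stated criterion removes a validly randomised patient whose Screening culture proves negative. Whether any such patient will be in PP depends on a committee decision under a plan not available here.

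If they are included, the exposure is in the PP responder comparisons and the early visits of the exploratory PP MMRM. The illustrative loss from a 20-point responder difference runs from 0.5 to about 4 points. The lower figure assumes that the Phase 2 denominators are Micro-ITT and that the whole shortfall entered PP this way. The upper figure assumes full enrolment of 234, with all 48 planned exclusions entering PP as failures and nobody else leaving it; not every exclusion would be a pending-culture case, so it is a bound, not an expectation.

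It would be wrong to carry this over to the trial's main conclusions. The primary analysis is in Micro-ITT, as is culture conversion, and type I error is untouched.

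**What to change.** Before Phase 3 unblinding, change the starting set in SAP 3.2.4 from the ITT Population to the Micro-ITT Population, keeping the condition on important deviations that bear on the primary efficacy assessment. List the change in SAP Section 5, since it departs from Protocol 8.1.

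In the same edit, settle whether PP requires study completion. The SAP has that condition, Protocol 8.1 does not, and Section 5 does not list the difference.

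The cost is a phrase in the SAP and a line in Section 5. The PP set may be slightly smaller. Made after Phase 3 unblinding, the same change would have to be documented as a deviation in a post hoc addendum or the CSR, under SAP Section 1.
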